### **2.7.3 Handling of missing values/censoring/discontinuations**

Missing baseline data (if applicable) for the secondary endpoints will not be imputed.

Missing follow-up data for the secondary endpoints will be handled as follows:

If a patient stayed on randomized study treatment for less than 24 weeks, missing data will not be imputed, and if data are available (which is not expected as per protocol) they will not be included in the analysis.

If a patient stayed on randomized study treatment for at least 24 weeks, but follow-up data are not available, data will be imputed by multiple imputation (see Section 5.1.4).

[figure not shown]
If a patient stayed on randomized study treatment for at least 24 weeks, and follow-up data are available, data will be used as observed, even if treatment was discontinued prior to Week 48.

Due to the COVID-19 pandemic, it was not possible for some patients to return in time for the Week-48 visit to perform a liver biopsy. Instead, it was possible for additional treatment to be dispensed (see drug dispensing plan in Section 5.5.2 in the protocol), and the Week-48 liver biopsy could be delayed up to approximately 12 weeks. Since the purpose of the secondary efficacy analysis is to evaluate the potential histological benefit of study treatment, all biopsies obtained, including those from eligible patients after Week 48, will be included in the analysis as Week-48 biopsies.

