6.2.6 Liver evaluation

6.2.6.1 Liver biopsy

[figure not shown]
Patients must have histologic evidence of NASH and liver fibrosis stage 2 or 3 (NASH clinical research network (CRN) staging criteria) demonstrated on liver biopsy during the Screening period. Alternatively, a historical biopsy can be used if performed within 6 months prior to screening, if:

- the patient has been receiving any of the therapies listed in [Table 5-4](#), the dose must have been stable (since 1 month before the biopsy up to and including screening),
- the patient weight has been stable (maximum weight loss of 10% since biopsy up to and including screening).

Five to eight Baseline Biopsy slides, unstained and prepared from biopsies performed during the screening period or \leq 6 months prior to the screening visit, will be sent to a Central Reader to determine eligibility. Patients will be treated for 48 weeks and an end of treatment biopsy will be performed and slides submitted to the Central Reader. A manual detailing all the requirements will be supplied to each study site.

For the patients who do not have an historical liver biopsy, [REDACTED] may be a useful pre-screening tool prior to liver biopsy for cases of indeterminate clinical NASH (F2/F3) diagnosis.

In case of premature treatment discontinuation, the end of treatment biopsy should only be performed if the patient has received at least 24 weeks of study treatment.

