9.5 Analysis of secondary variables

9.5.1 Efficacy variables

An overview of the secondary efficacy variables and planned analysis is given in [Table 9-2](#).

Table 9-2 Secondary efficacy variables and analyses

Variable	Analysis
At least a one point improvement of fibrosis	Cochran-Mantel-Haenszel test controlling for baseline fibrosis stage for each tropifexor + CVC combination vs. each monotherapy treatment, with supporting information from risk differences, odds ratios with 95% confidence intervals
Resolution of steatohepatitis (as determined by central pathologist)	Cochran-Mantel-Haenszel controlling for baseline fibrosis stage for each tropifexor + CVC combination vs. each monotherapy treatment, with supporting information from risk differences, odds ratios with 95% confidence intervals

There is a single secondary objective in this study which is to characterize the efficacy of tropifexor + CVC in patients with NASH with fibrosis stage F2/F3 as assessed by histological improvement after 48 weeks of treatment compared to monotherapies (tropifexor and CVC) relative to baseline biopsy. There are two estimands that will be used to evaluate this objective.

The first estimand is the difference on the proportion of patients on the different tropifexor + CVC regimens who achieve at least a one point improvement in fibrosis at Week 48 compared to tropifexor and CVC monotherapy patients. It is assumed that anyone who does not have a Week 48 liver biopsy or does not remain on their randomized study treatment for at least 24 weeks (even if a Week 48 biopsy was obtained) will have their outcome imputed by multiple imputation (MI). For subjects who remain on their randomized study treatment for at least 24 weeks, but discontinue study treatment prior to Week 48, available Week 48 biopsy results will be used as observed. This is a hypothetical strategy addressing the question “what would be the outcome if subjects had stayed at least 24 weeks on treatment and a Week 48 biopsy had been obtained”. Treatment differences between tropifexor + CVC combination therapy and monotherapy with tropifexor or CVC will be evaluated using a Cochran-Mantel-Haenszel test controlling for baseline fibrosis stage (F2/F3). The estimand will be evaluated in the FAS population.

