The second estimand is the difference in the proportion of patients on the different tropifexor + CVC regimens who achieve resolution of steatohepatitis at Week 48 relative to baseline compared to tropifexor and CVC monotherapy patients. It is assumed that anyone who does not have a Week 48 liver biopsy result or does not remain on their randomized study treatment for at least 24 weeks will have their outcome imputed by multiple imputation (MI). The handling of intercurrent events (discontinuation of assigned treatment) is equivalent to the first estimand as described above. Treatment differences between tropifexor + CVC combination therapy and monotherapy with tropifexor or CVC will be evaluated using a Cochran-Mantel-

Haenszel test controlling for baseline fibrosis stage (F2/F3). The estimand will be evaluated in the FAS population.

Due to COVID-19 pandemic, it may not be possible for patients to return on time for Week 48 visit to perform liver biopsy and according to drug dispensing plan in [Section 5.5.2](#), the Week 48 liver biopsy can be delayed by approximately 10 weeks. Since the purpose of the secondary efficacy analysis is to evaluate the potential histological benefit of study treatment, all biopsies obtained, including those from eligible patients after week 48, will be included in the analysis.

Sensitivity analyses:

Sensitivity analyses will be conducted to account for delayed Week 48 biopsies due to extended treatment under COVID-19 pandemic. Further details are to be described in the statistical analysis plan (SAP).

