### 2.7.2 Statistical hypothesis, model, and method of analysis

The two secondary endpoints are incorporated in two estimands.

The first estimand is defined as below:

- Treatment: The randomized treatment (tropifexor 140 µg once-daily, CVC 150 mg once-daily, tropifexor 140 µg + CVC 150 mg once-daily, and tropifexor 90 µg + CVC 150 mg once-daily) taken for 48 weeks, further defined in Section 5.2 in the protocol.
- Population: Full analysis set.
- Endpoint: Proportion of patients who have at least a one-point improvement in fibrosis.
- Summary measure: Difference in the proportion of patients on the different tropifexor + CVC regimens who achieve at least a one-point improvement in fibrosis at Week 48 biopsy compared to tropifexor and CVC monotherapy patients.

The second estimand is the same as the first one except

- Endpoint: Proportion of patients with resolution of steatohepatitis

- Summary measure: Difference in the proportion of patients on the different tropifexor + CVC regimens who achieve resolution of steatohepatitis at Week 48 relative to baseline compared to tropifexor and CVC monotherapy patients.

Both estimands will be evaluated using a Cochran-Mantel-Haenszel test controlling for baseline fibrosis stage (F2/F3). Risk differences and odds ratios with 95% confidence intervals will provide supporting information for both estimands.

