## 4 Change to protocol specified analyses

- AE and SAE summary by the onset time with respect to COVID-19 pandemic in different countries and regions are added.
- Paired-biopsy reading will be used for all biopsy-based outputs.
- NAS-based definition of resolution of steatohepatitis is added in the supportive analyses for secondary efficacy endpoint [REDACTED]

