### **5.1.4 Other imputations**

A multiple imputation approach will be applied to missing follow-up biopsies.

For subjects who do not have a Week 48 liver biopsy or not remain on their randomized study treatment for at least 24 weeks (even if a Week 48 biopsy was obtained), the biopsy based outcomes will be imputed by multiple imputation (MI). It is assumed that biopsy results are missing at random (MAR). Available results for subjects who discontinue treatment before 24 weeks are set to missing for this analysis. Imputation will be based on available results from subjects who did not discontinue study treatment, thus addressing the question what the results would have been if subjects had not discontinued. The imputation model will take into account the treatment group, the baseline fibrosis stage (categorical), [REDACTED], the baseline ALT, [REDACTED] and change in ALT, [REDACTED] from baseline to Week 12 and to Week 24 (continuous). As there is only one post-baseline biopsy assessment, an arbitrary missing pattern is assumed and a fully conditional specification (FCS) method with logistic regression is applied. The randomization seed is 4572201 and the number of imputations will be set to 50.

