## 5.6 Other statistical aspects

### Secondary efficacy endpoints

Multiple imputation is adopted to impute missing Week 48 biopsy results for eligible patients. See Section 5.1.4 for more details.

CMH test is adopted for inference controlled for the baseline fibrosis stage (F2/F3). In order to pool results from multiple imputation, test statistic of CMH test is transformed using Wilson-Hilferty transformation

$$ST_{WH\_CMH^{(m)}} = \frac{\sqrt[3]{CMH^{(m)}/df} - (1 - \frac{2}{9 * df})}{\sqrt[2]{2/(9 * df)}}$$

Where  $CMH^{(m)}$  is the CMH test statistic computed from the  $m$ -th imputed dataset,  $df$  is the degrees of freedom associated with the test statistic, and  $ST_{WH\_CMH^{(m)}}$  follows approximately standard normal distribution. Consequently, the test results obtained from multiple imputation datasets can be combined by specifying the model effects and standard error in PROC MIANALYZE in SAS and the final one-side  $p$ -value for CMH test can be obtained.

Odds ratio and relative risk obtained from PROC FREQ also need to be transformed to normal distribution before pooling. Both statistics are log-normally distributed and hence a simple log transformation would transform them to normal and similar procedure to the above can be followed to obtain the pooled results. Finally, exponential transformation is implemented to transform the statistics and their CI back to the original scale.

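### SAP 2.7.3 drops patients with under 24 weeks on treatment from the histology analyses, while SAP 5.1.4 and Protocol 9.5.1 impute them within the FAS

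*SAP*

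**What the plan says.** - **SAP 2.7.3:** "If a patient stayed on randomized study treatment for less than 24 weeks, missing data will not be imputed". The same sentence keeps any biopsy data from such a patient out of the analysis. Multiple imputation (MI) is reserved for patients with at least 24 weeks on treatment and no follow-up biopsy, with a reference to 5.1.4 for the method.
- **SAP 5.1.4:** for patients with no Week 48 biopsy, or with less than 24 weeks on randomized treatment ("even if a Week 48 biopsy was obtained), the biopsy based outcomes will be imputed by multiple imputation (MI"). A result that exists for an early stopper is first set to missing.
- **Protocol 9.5.1, first estimand (fibrosis):** the same two groups of patients ("even if a Week 48 biopsy was obtained) will have their outcome imputed by multiple imputation (MI"). The protocol calls this a hypothetical strategy, evaluated in the FAS.
- **Protocol 9.5.1, second estimand (resolution of steatohepatitis):** those without a Week 48 result, or not on randomized treatment "for at least 24 weeks will have their outcome imputed by multiple imputation (MI".
- **SAP 2.7.2:** "Population: Full analysis set".
- **SAP 5.6:** "Multiple imputation is adopted to impute missing Week 48 biopsy results for eligible patients". It does not say who is eligible.
- **SAP Section 4** lists three changes to the protocol analyses, for example "Paired-biopsy reading will be used for all biopsy-based outputs". No visible entry concerns early stoppers.
- **Protocol 6.2.6.1:** after premature discontinuation, "the end of treatment biopsy should only be performed if the patient has received at least 24 weeks of study treatment".

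**The concern.** The sections agree that an early stopper's observed biopsy is not used. They disagree on what follows: the patient is either dropped or imputed. Because no end-of-treatment biopsy is planned before 24 weeks of treatment, essentially every early stopper falls under the conflict.

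The two rules answer different questions. Imputation targets all FAS patients under the protocol's hypothetical strategy. Dropping leaves a comparison among patients who stayed at least 24 weeks, a group formed after randomisation, so the arms compared are no longer the randomized ones.

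The denominator, the estimate and the Cochran-Mantel-Haenszel (CMH) p-value of both endpoints depend on which section is programmed. So do the supportive analyses in SAP 2.7.4 that repeat the 2.7.2 analyses. If the text stays as it is, the choice is still open when treatment codes become known.

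**Working it through.** **1. The rules side by side, for a patient with under 24 weeks on treatment**

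| Source | No biopsy | Biopsy available | In the comparison? |
|---|---|---|---|
| SAP 2.7.3 | not imputed | not used | no outcome contributed |
| SAP 5.1.4 | imputed | set to missing, then imputed | yes |
| Protocol 9.5.1 | imputed | imputed | yes, in the FAS |

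SAP 2.7.3 does not call these patients non-responders. With nothing imputed and nothing used, they cannot enter the CMH table.

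**2. The plan's own power figure**

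Inputs (Protocol 9.8.2, SAP 3.2): 50 per arm, two-sided 0.10, continuity-corrected chi-square, 69% on the combination against 42% (tropifexor) and 35% (CVC). With d the difference in rates, the uncorrected size equivalent to n corrected patients per arm is m = (n − 1/d)²/n.

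- Against tropifexor, d = 0.27: m = (50 − 3.70)²/50 = 42.9, power 81.7% (stated 81%).
- Against CVC, d = 0.34: m = (50 − 2.94)²/50 = 44.3, power 95.1% (stated 95%).

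These figures assume an outcome for all 50 patients. If early stoppers are dropped, corrected power against tropifexor is 77.3% at 45 per arm (10% stopping) and 72.0% at 40 per arm (20%).

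**3. Patients affected**

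The documents give no stopping rate, so 10–20% is an assumption. With the 193 randomized patients (protocol, Amendment 3): 193 × 0.10 = 19.3 and 193 × 0.20 = 38.6.

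**4. How an arm's rate moves**

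Let f be the share stopping early and g the stayers' response rate minus the rate imputed for stoppers. The FAS rate equals the stayers' rate minus f × g. With assumed gaps of 10–20 points, the shift is between 0.10 × 10 = 1 point and 0.20 × 20 = 4 points per arm. The shift in the risk difference is the difference between the two arms' f × g. It is close to zero when stopping is alike in both arms, and not when it differs.

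**5. Simulation with random stopping**

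Set-up: 2,000 trials per scenario, 50 per arm, F2/F3 50:50, response depending on arm and one standard-normal predictor (assumed log-odds slope 0.6). Exclusion uses CMH by stage. MI uses logistic imputation on arm, stage and predictor, 50 imputations, with CMH pooled by the Wilson-Hilferty transformation. The threshold is p < 0.10.

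| Rates | Stopping | Mean absolute change in risk difference | 95th percentile | Calls that differ |
|---|---|---|---|---|
| 42% vs 69% | 10% | 0.82 points | 2.11 | 1.8% |
| 42% vs 69% | 20% | 1.20 | 3.27 | 3.4% |
| 42% vs 69% | 25% | 1.44 | 3.97 | 3.8% |
| 35% vs 53% | 10% | 0.81 | 2.15 | 3.3% |
| 35% vs 53% | 20% | 1.21 | 3.24 | 4.8% |
| 35% vs 53% | 25% | 1.51 | 3.88 | 5.2% |

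For 42% vs 69%, power under exclusion and under MI was 81.5% and 82.3% at 10% stopping, and 75.5% and 76.5% at 25%. These come from an uncorrected CMH test, so they compare the two rules with each other and must not be set against the plan's 81%.

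**6. Unequal stopping (10% monotherapy, 20% combination; 42% vs 69%)**

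MI minus exclusion is −1.41 points if stoppers are 1 SD worse on the predictor (calls differ in 5.1%) and +0.53 points if they are 1 SD better (4.5%).

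A separate large-population calculation let patients with a poor early predictor value stop more often, with the response slope at 0.5 to 1.0. With equal stopping (10% or 20%), exclusion stays at about 27 points. At 10%/20% it gives 27.8 to 28.6 points against 27.0 in the full FAS; at 10%/30% it gives 28.6 to 30.1.

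**7. A related gap in SAP 5.1.4**

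Imputation draws on patients who did not discontinue treatment. The section does not say whether this includes those who stopped between Weeks 24 and 48, whose biopsies Protocol 9.5.1 and SAP 2.7.3 use as observed. The hypothetical question also differs: the protocol supposes at least 24 weeks on treatment and a Week 48 biopsy, while the SAP supposes no discontinuation.

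**The case against.** The documents do lean one way. The SAP says it implements the protocol, the protocol has one rule for both estimands, and SAP 5.1.4 repeats it with model, seed and number of imputations. Section 2.7.3 looks like a paragraph that was not aligned. The endpoints are secondary, the trial has no formal hypotheses, and the sample size rests on feasibility. The average shift is below the 2 points that one patient represents in an arm of 50. The 0.10 level appears only in the power sections; the analysis sections give CMH tests with 95% intervals and set no decision threshold. The simulation uses one invented predictor, because the planned imputation model is partly blacked out.

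Most of this stands as a limit on size, and the figures are illustrations. It does not remove the contradiction. No text says which SAP section prevails, and 2.7.3 reads as deliberate, since it notes that such data are not expected. That 2.7.3 excludes the patients is a reading, but no other treatment of them is given there. Declaring exclusion in Section 4 would also end the contradiction, but it would replace the FAS estimand with a comparison of patients selected after randomisation. The donor-set and wording points are accurate but minor.

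**Conclusion.** The concern holds and needs fixing before unblinding. The reason is not a large bias: it is that one set of planned between-arm efficacy tests has two incompatible algorithms, one of which departs from the protocol undeclared. Under assumed random stopping of 10–25%, the choice moves the risk difference by 0.8–1.5 points on average (95th percentile 2.1–4.0) and changes the call at 0.10 in 1.8–5.2% of simulated trials. Under assumed unequal stopping, the simulated shift runs from −1.4 to +0.5 points, and the large-population calculation reaches about 3 points at 10%/30%. The actual size and direction cannot be known from the documents, because they give neither stopping rates nor stoppers' expected response.

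**What to change.** - **SAP 2.7.3:** state that patients with less than 24 weeks on randomized treatment have any biopsy result set to missing, are imputed by MI, and stay in the FAS denominator, as in Protocol 9.5.1 and SAP 5.1.4.
- **Exclusion:** if wanted, keep it only as a labelled supportive analysis.
- **SAP 5.6:** replace the undefined reference to eligible patients with the same definition.
- **SAP 5.1.4:** say whether patients who stopped between Weeks 24 and 48 are among those on whom the imputation is based, and word the hypothetical question as the protocol does.

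This is wording in one SAP amendment before unblinding. It needs no new data, and the imputation model and pooling are already specified in SAP 5.1.4 and 5.6.

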### **2.7.4 Supportive Analyses**

Since that some Week-48 biopsies may not be obtained as originally scheduled, the same endpoints as in Section 2.7.2 will be re-evaluated. Summary tables will be provided for corresponding summary measures by treatment group and by whether the patients received extended treatment.

In addition, the same endpoints as in Section 2.7.2 will be re-evaluated for patients with at least 10% weight loss at Week 48 compared to Baseline. Summary tables will be provided for corresponding summary measures by treatment group and by population with or without at least 10% weight loss at Week 48 compared to Baseline.

Analyses of proportion of patients who have at least one-point improvement in fibrosis described in Section 2.7.2 and corresponding supportive analyses described in Section 2.7.4 will be repeated based on modified ISHAK scoring system.

Analyses of both secondary efficacy endpoints described in Section 2.7.2 and corresponding supportive analyses described in Section 2.7.4 will be repeated based on real-time biopsy reading.

Qualitative results of comparison between biopsies obtained during Screening and Week 48 based on paired biopsy readings will be summarized by treatment group into three categories (better, same, [REDACTED]) for following parameters: steatosis, [REDACTED] NASH CRN fibrosis, and modified ISHAK score.

## 2.8 Safety analyses

The analysis of safety parameters will be performed in the Safety Analysis Set.

### 2.8.1 Adverse events (AEs)

Treatment emergent adverse events (events started after the first dose of study treatment or events present prior to the first dose of study treatment but increased in severity based on preferred term, until EOS visit or 30 days after EOT visit, whichever comes earlier) will be summarized. AEs will be summarized by presenting, for each treatment group, the number and percentage of patients having experienced

- Any adverse event (AE),
- Any serious adverse event (SAE),
- Any adverse event by primary system organ class (SOC),
- Any adverse event by preferred term (PT),
- Any adverse event by severity,
- Any adverse event possibly related to study treatment (investigator assessment),
- Any adverse event resulting in discontinuation of study treatment,
- Any adverse events of special interest for tropifexor or CVC treatment,
- Any adverse events by onset time before and after the start date of COVID-19 pandemic by country/region,
- Any serious adverse events by onset time before and after the start date of COVID-19 pandemic by country/region.

If a patient reported more than one adverse event with the same preferred term, the adverse event with the greatest severity will be presented. If a patient reported more than one adverse event within the same primary system organ class, the patient will be counted only once with the greatest severity at the system organ class level, where applicable.

The start date of COVID-19 for different countries or regions is defined in Table 5-1 of “COVID-19 (Coronavirus) Guidance - Start and End Dates by Region for Sensitivity Analyses” Version 1.0 released on May 19, 2020. As of the time of finalization of this SAP, the start (and end) dates are listed below:

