### 2.5.4 Supportive analyses

Supportive analyses are added for evaluation of the impact of COVID-19 on study results. See [Section 2.8.1](#).

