**Table 2-3 Defined Dates**

Region/Country	Start Date	End Date
Italy	23-Feb-2020	End date has not yet been defined
Rest of the World	01-Mar-2020	End date has not yet been defined

Tabulations of adverse events, SAE, and adverse events of special interest broken down by time of onset according to the following intervals will be provided as well:

- Starting within 4 weeks after first administration of study treatment,
- Starting between 4 weeks and 12 weeks after first administration of study treatment,
- Starting more than 12 weeks after first administration of study treatment.

*For the legal requirements of ClinicalTrials.gov and EudraCT, two required tables on treatment emergent adverse events which are not serious adverse events with an incidence greater than or equal to 5% in any treatment group and on treatment emergent serious adverse events and SAE suspected to be related to study treatment will be provided by system organ class and preferred term on the safety set population.*

*If for a same patient, several consecutive AEs (irrespective of study treatment causality, seriousness and severity) occurred with the same SOC and PT:*

- *a single occurrence will be counted if there is  $\leq 1$  day gap between the end date of the preceding AE and the start date of the consecutive AE*
- *more than one occurrence will be counted if there is  $> 1$  day gap between the end date of the preceding AE and the start date of the consecutive AE*

*For occurrence, the presence of at least one SAE / SAE suspected to be related to study treatment / non SAE has to be checked in a block e.g., among AE's in a  $\leq 1$  day gap block, if at least one SAE is occurring, then one occurrence is calculated for that SAE.*

*The number of deaths resulting from SAEs suspected to be related to study treatment and SAEs irrespective of study treatment relationship will be provided by SOC and PT.*

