### Crude incidence and related risk estimates

For  $n$  patients each at risk to experience a certain event with probability  $\pi$ , the crude incidence is estimated as  $p=x/n$ , where  $x$  is the number of patients with the event.

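### The COVID-19 before/after and onset-interval adverse event tables give no number at risk or person-time, so their percentages cannot be compared across windows; the SAP also omits, without saying so, the exposure-adjusted tables promised in the protocol

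*SAP*

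**What the plan says.** SAP 2.8.1 defines the adverse event summaries as "for each treatment group, the number and percentage of patients having experienced" each item on a list. One item is "Any adverse events by onset time before and after the start date of COVID-19 pandemic by country/region", and another does the same for serious adverse events. The start date is 23 February 2020 for Italy and 1 March 2020 elsewhere, with no end date (Table 2-3). SAP 2.8 sets the population: "The analysis of safety parameters will be performed in the Safety Analysis Set". It makes no restriction to patients under observation in a period.

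After Table 2-3, the SAP adds tabulations of adverse events, serious adverse events and events of special interest in three onset intervals. The first is "Starting within 4 weeks after first administration of study treatment", the second runs from 4 to 12 weeks, and the last is "Starting more than 12 weeks after first administration of study treatment". No denominator is stated for these.

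The purpose of the pandemic tables is given in SAP 2.5.4: "Supportive analyses are added for evaluation of the impact of COVID-19 on study results". That section points only to 2.8.1, and protocol 9.4.4 plans no sensitivity analysis of the primary variables.

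Protocol 9.5.2.1 commits to exposure-adjusted adverse event tables as well as tables by interval. SAP 2.8.1 keeps the interval tables and does not mention exposure adjustment. SAP section 4, which lists departures from the protocol, does not record this.

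**The concern.** The primary objective is safety, with no hypotheses or models, so the descriptive tables are the primary result. The pandemic tables are there to be read before against after, and the onset tables invite reading early against late. A crude percentage supports such a reading only if the windows offer similar observation time to similar numbers of patients.

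They do not. The onset windows last 4 weeks, 8 weeks and about 40 weeks, and the last is longer for patients whose treatment was extended. In the pandemic split, each patient's time on either side of the date is fixed by the randomisation date. A patient who finished before March 2020 has no time after it, and one randomised later has none before it. A difference between columns may therefore reflect only the length of observation. For the primary safety results, the plan has no other check on the pandemic's effect.

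**Working it through.** The plan states no figure for these tables, so there is none to reproduce. The check asks what the tables would show if the event rate never changed.

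**Inputs from the documents.** Onset windows of 0–4, 4–12 and over 12 weeks (SAP 2.8.1). Counting of events stops at the end-of-study visit or 30 days after the end-of-treatment visit, whichever is earlier (SAP 2.8.1), which is about Week 52 for a completer. Cut date 1 March 2020. 193 patients randomised, with enrolment complete when protocol version 03 was issued, dated 7 May 2020 in SAP section 1. About 50 patients per arm.

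**Assumptions, not in the documents.** A constant event rate; the cumulative incidences shown below; uniform enrolment between the dates shown; 52 weeks of observation each; no dropout unless stated.

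**Formula.** The probability of at least one onset in a window of w weeks is 1 − exp(−h·w), with h the weekly rate.

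**Onset intervals, shown as percentages of the arm**

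- If 80% have an event in 48 weeks: h = −ln(0.2)/48 = 0.0335. The windows give 1 − exp(−4h) = 12.6%, 1 − exp(−8h) = 23.5% and 1 − exp(−40h) = 73.8%.
- If 30% have an event in 52 weeks: h = −ln(0.7)/52 = 0.00686. The windows give 2.7%, 5.3% and 24.0%, or 1.4, 2.7 and 12.0 of 50 patients, which is an 8.9-fold apparent rise.
- The same 30% event with 20% dropout: 2.7%, 5.2% and 21.0%, with 50, 49.1 and 47.5 patients at risk at the start of each window.
- Over incidences of 10% to 95% and dropout of 0% to 30%, the last-to-first ratio runs from 3.7 to 9.8. It is always a rise.

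**Pandemic split, 30% event over 52 weeks, whole-group denominator**

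| Assumed enrolment | Mean weeks before / after | Before | After |
|---|---|---|---|
| Sep 2018 to mid-Nov 2019 | 41.4 / 10.6 | 24.4% | 6.7% |
| Mar 2019 to Mar 2020 | 26.1 / 25.9 | 16.0% | 15.8% |
| Jun 2019 to 7 May 2020 | 15.7 / 36.3 | 9.9% | 21.7% |

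The underlying rate is the same in all six cells. In the first row, 193 patients are at risk before the date and 112 after it.

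**Changing only the denominator.** In the first row, restricting the later column to patients still under observation gives 24.4% against about 11.6%. The gap narrows but stays, because those patients still have less time after the date than before it.

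**Using person-time.** The same event gives 0.00686 × 100 = 0.69 per 100 patient-weeks, or about 36 per 100 patient-years, in every onset window and on both sides of the date. The false change disappears.

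**The case against.** Several points on the other side stand.

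- A reader might infer that the pandemic tables are bound to show a change. The documents do not support that: they give no randomisation dates, and the second row of the table shows no visible difference.
- A reader might take a whole-arm denominator as stated for both sets of tables. It is the direct reading for the pandemic items, which fall under the number-and-percentage instruction. The interval text only promises tabulations, and SAP 5.6 defines crude incidence over patients at risk without defining that group by window. For those tables the denominator is unstated.
- A reader might infer that a poorly tolerated arm would look safer late. If 15% of an arm had no observation after Week 12, 73.8% would become 0.85 × 73.8 = 62.8%. That is an upper bound. Counting can run to 30 days after the end-of-treatment visit, so a patient who stops after about Week 8 can still contribute late events. Protocol section 6 also asks early stoppers to attend the planned Week 48 and Week 52 visits, although protocol 5.6.1 places the safety visit 4 weeks after the last dose. Nothing in the documents shows that stopping differs by arm.
- The primary objective compares arms. Within one window, randomised arms share the same window length and, in expectation, the same calendar split. That comparison is largely sound unless discontinuation differs, and the SAP reports discontinuation and exposure by arm elsewhere.
- The SAP says it implements the protocol, so the commitment to exposure-adjusted tables may still hold. A deliberate withdrawal cannot be inferred from silence. Even so, the SAP should carry the commitment or record its removal, and the protocol wording does not clearly extend exposure adjustment to the separate windows.

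None of this makes the percentages comparable across windows, and comparison across windows is the stated use of the pandemic tables.

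**Conclusion.** The point holds as a limit on what these tables can show. As planned, they cannot tell a change in event rate from a difference in observation time. For the onset intervals the distortion follows from the fixed window lengths: under a constant rate, percentages of the arm rise about 4- to 10-fold from first to last window over the range examined. This assumes that the arm is the denominator. For the pandemic split, the size and direction cannot be fixed from the documents; a fall, no change and a rise all arise under plausible enrolment dates.

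The omission of the exposure-adjusted tables is a separate, documented gap between protocol 9.5.2.1 and the SAP. The change should be made, but it is not critical: the tables are descriptive, and no type I error rate, sample size or efficacy result depends on them.

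**What to change.** In SAP 2.8.1:

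1. Restore the exposure-adjusted adverse event tables of protocol 9.5.2.1, or list their removal with a reason in SAP section 4.
2. For each pandemic period and each onset interval, report by arm, beside the counts, the number of patients at risk, the patient-time in the window, and the incidence as patients with a first event in that window per 100 patient-years at risk, with a 95% confidence interval. Count time at risk from entry into the window to the first event in it or the end of treatment-emergent observation.
3. Do not rely on an at-risk denominator alone, since it leaves unequal window length uncorrected.
4. State that the before/after rates remain confounded with time on treatment, because later calendar time is also later treatment time for each patient, and that they are descriptive.

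The cost is a little extra programming. The dates needed are already collected.
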